3.2.2 EXCLUSION CRITERIA FOR PARTICIPANTS (MEN)

- 1. Suitable for or attending an existing probation-based perpetrator intervention.
- 2. Man involved with the private family law court.
- 3. History of sex offences against children.
- 4. Answers 'strongly disagree' to all 8 items on the eHealth Literacy Scale (eHEALS).
- 5. Substance use impairs ability to take part in the trial (based on practitioner assessment of frequency/amount of substance use, impact of substance use on daily activities/functioning, and health, social, legal or financial problems as a result of substance use) assessed using the substance use screen (England) or SARA V3 (Scotland).

3.2.3 INCLUSION CRITERIA FOR CURRENT OR EX-PARTNERS (WOMEN)

- 1. Adult (18+) women who have a current or ex-partner participating in the trial that was sentenced for IPV towards them.
- 2. Lives in the UK.
- 3. Able to communicate in and understand English for the purpose of research interviews.

3.2.4 EXCLUSION CRITERIA FOR CURRENT OR EX-PARTNERS (WOMEN)

- 1. Current order preventing her from contacting current or ex male partner recruited to the trial.
- 2. Other safety concerns that may put the male partner at risk. These will be considered on a case-by-case basis by the research team and the clinical team e.g. where both participants share a mobile phone number, the female participant has a court case pending for IPV or there is a child protection hearing pending.
- 3. Female partner discloses that there is an order preventing her male current or ex-partner from contacting her (i.e. contradicting what he has said in his screening interview). In such cases the man would not be withdrawn, unless the clinical team felt there was an increased risk to either party in his continuing in the study.

3.2.5 INCLUSION CRITERIA FOR STAFF

For PP/JSW

- 1. Identified men for ADVANCE-D; or
- 2. Supervising officer for men on ADVANCE-D.

For facilitators and partner support workers

- 1. Trained and certified to deliver ADVANCE-D or partner support for ADVANCE-D.
- 2. Delivered or attempted to deliver ADVANCE-D or partner support for ADVANCE-D.

3.2.6 INCLUSION CRITERIA FOR PDU/ JSWT

- 1. PDU/ JSWT must have a central intervention delivery model (e.g. a central intervention delivery team in Greater Manchester deliver interventions across all 9 PDU).
- 2. PDU/ JSWT must have trained and certified ADVANCE-D facilitators and partner support workers.

3.2.7 EXCLUSION CRITERIA FOR PDU/JSWT

1. PDU/JSWT must not be participating sites in other intervention trials.

3.3 INFORMED CONSENT

For participants

Men who have received a community sentence for IPV from a judge or who have been released on license from prison after serving a sentence for IPV, must present to a PDU/JSWT where decisions on the CJOM required to address any treatment/support recommended by court or license conditions will be made. All men will be screened against the eligibility criteria by a probation practitioner (PP) or justice social worker (JSW)

during first presentation to the PDU/ JSWT. All men presenting to PDU/ JSWT will routinely be assessed for alcohol or drug misuse using the Spousal Risk Assessment (SARA)⁶³ V2 (England) or V3 (Scotland) and the Offender Assessment System (OASys) completed by PP (England) or the Level of Service/Case Management Inventory (LS/CMI) completed by JSW (Scotland).

Men who are eligible will be invited to take part in the trial by their PP/ JSW. PP/ JSW will receive training on gaining informed consent, that emphasises participation is voluntary, and be provided with a script about the study and its aims. PP/ JSW will:

- 1. Read the participant information sheet (PIS), explain what taking part involves and that taking part is voluntary.
- 2. Provide men with a copy of the PIS.
- 3. Invite men to participate in the research (baseline, 4- and 12-month follow-up interviews, qualitative interviews and data linkage at 24-months).
- 4. Explain limitations to confidentiality.
- 5. Inform them their (ex)-partner will be contacted to provide outcome data and offered support.

As the decision about CJOM required to address any treatment/support will be made on the second meeting with the PP/ JSW post court/release - men will need to decide whether they wish to participate in the trial at that meeting. This will give them approximately a week to decide whether they wish to take part in the trial. At the next visit, PP/ JSW will then gain informed consent from men agreeing to take part in the trial. Consent forms will be counter-signed in triplicate by both the male participant and the PP/ JSW. Participants will receive a copy of the signed consent form; a copy will be filed in the Investigator Site File and a copy will be returned to the local research team and stored in a locked filing cabinet.

A researcher will then text or call the consented participant and complete the baseline interview with the participant in person at the PDU/JSWT or by phone or video call. All men from a cluster should be baselined within two weeks. This call will not be undertaken in the presence of a PP/ JSW. During this call, researchers will check the participant still wishes to take part in the trial, that they have consented to take part in the trial of their own free will and are fully informed of what taking part in the study involves. Participants will have the opportunity to opt out of the trial at this point without any repercussions to their CJOM. This timeframe allows the participant up to two weeks from consenting to take part to decide whether they still wish to take part.

A researcher will be responsible for completing a baseline interview with consented men by phone, video conferencing, or in person at the PDU/JSWT. This will not be conducted in the presence of a PP/JSWT. Interviews will never be conducted in participants' homes.

Only after the men are consented and baselined in each PDU /JSWT and their female current or expartners have been consented and baselined; will participants and PDU/ JSWT team be told what treatment arm they have been allocated to.

For current or ex-partners

The PP/ JSW will securely pass the contact details of victims/ survivors to the trial manager using a password protected document via encrypted e-mail, a secure Microsoft Teams channel or via another secure method (e.g. Criminal Justice Secure Email). This is standard practice in community perpetrator interventions to ensure safeguarding and risk are managed and is included in the Home Office Standards for Domestic Abuse Perpetrator Interventions.⁶⁴ The Information Commissioner's Office have stated that a service can potentially use legitimate interest as a lawful basis to gather this information suggesting the individual (ex)-partner would reasonably expect you to use their data in this way (Case Reference Number ENQ0782120). Researchers need current or ex-female partners' details to invite them to take part in the research by providing outcome data, and to share their details with the women's support service who will contact them to offer support, assess risk and signpost for additional needs. Clear and regular lines of communication between probation/justice social work, women's support services and the research team are necessary so that any changes in risk can be identified and appropriate actions taken to ensure that current and ex-female partners are effectively safeguarded. While all current and/or ex-partners of men in the ADVANCE-D intervention will be offered support, only the current or ex-partner connected to the index IPV event will be recruited to the study. Following male participants' baseline assessment, researchers will text or email their (ex)-partners with brief information about the study and advise that they will be phoning them. A

script and short explanation video about taking part in the study has been developed with the women's people with lived experience panel to facilitate this.

To maximise safety and convenience, there will be the option to select a time slot for the call. Within a week, a researcher will contact the (ex)-partners to:

- 1. Inform them their (ex)-partner is participating in the study.
- 2. Read the PIS and explain what taking part involves.
- 3. Invite them to participate in the research (baseline and follow up interviews, qualitative interviews and data linkage at 24 months).
- 4. Explain limitations to confidentiality.
- 5. Advise them that an integrated support service (ISS) worker will call to offer them support only if their current or ex-partner is allocated to receive the ADVANCE-D Programme.

Women interested in taking part in the research will be emailed, sent a message on WhatsApp or mailed a copy of the PIS and consent form by the researcher. Before the baseline assessment takes place, the researcher will check with participants whether they have somewhere quiet and private to talk and ensure that they are safe to talk. Researchers will be responsible for recruitment, consent and baseline interviews with (ex)-partners. (Ex)-partners will be given the option for questionnaires to be administered by the researcher in person, by phone or video call. Face-to-face recruitment or interviews will take place in probation, women's support services or other services such as children's centres or libraries. The researcher that completes the questionnaires with the partner will be a different researcher to the one that completed the baseline assessment with the male participant to avoid inadvertent disclosure of information.⁹⁷ All research participants have the right to refuse to answer questions if they do not wish. Interviews will never be conducted in (ex)-partners' homes.

Only after recruitment and the baseline interview with (ex)-partners has been completed or the (ex)partner has declined the offer to participate in the trial or the (ex)-partner is not contactable, will the allocation of PDU/ JSWT be known to researchers and PDU/ JSWT.

Women whose current or ex-partners are in a PDU/ JSWT allocated to receive the ADVANCE-D Programme, will be contacted by an ISS worker to offer support regardless of whether the woman wishes to take part in the research. If researchers have been unable to contact the female (ex)-partners, they will pass the contact details to the ISS workers who will attempt to call them to offer support. Women whose current or ex-partners are in the control arm of the study will receive whatever the usual support to partners would be, if any.

For staff

Staff at each service involved in delivering the intervention (PDU or JSWT) or supporting women whose partners are receiving the intervention (ISS) will be invited to take part in focus groups or interviews throughout the duration of the study about their experiences. This process is explained to services as part of their contract when they agree to be involved in the study.

Staff will first receive an email from the researcher inviting them to take part in the research. This email will also contain the PIS and consent form. Researchers will follow-up this email with a phone call several days later to verbally explain the aims of the study to staff and ask whether they are interested in taking part. Staff will be asked to return a completed copy of the consent form by email to the researcher prior to taking part in a focus group or interview. The option to return the consent form by post will also be available. In line with HRA and MHRA joint statement on seeking and documenting consent using electronic methods (eConsent) – Health Research Authority (2018), staff will be able to select yes or no for each item on the consent form, type their name in the signature box and add the date they completed the form to confirm their consent.

If the consent form has not been returned, researchers can witness and audio record informed consent following reading through the PIS and all items on the consent form and record it in writing. Study consent forms will all be electronic (audio recordings or emailed Word document) and will be stored on SharePoint. A suitable time will be organised to undertake the focus group or interview.

Interviews with staff will take place in-person or by phone or video call. These interviews will be recorded with consent.

3.4 PARTICIPANT TIMELINE

3.4.1 *PARTICIPANTS (MEN)*

Timepoint																				e	e
	Week 0	Week 1	Week 2	Week 3	Week 4	Week 5	Week 6	Week 7	Week 8	Week 9	Week 10	Week 11	Week 12	Week 13	Week 14	Week 15	Week 16	Week 20	Month 4 post baseline	Month 12 post baseline	Month 24 post baseline
Screening and eligibility	X																				
2. Risk assessment	X																				
3. Consent		X																			
4. Arrange baseline interview		X																			
5. Registration and Baseline			X																		
6. ADVANCE-D																					
a. Individual goal setting				X																	
b. Welcome to ADVANCE-D group					X																
c. Follow-up call					X																
d. ADVANCE-D group session						X		X		X		X		X		X					
e. ADVANCE-D website session						X	X	X	X	X	X	X	X	X	X	X	X				
f. ADVANCE-D individual coaching						X	X	X	X	X	X	X	X	X	X	X	X				
g. ADVANCE-D booster																		X			
7. Follow-up assessment																			X	X	1
8. Data linkage with health and criminal justice records																					X

Table 3. Schedule of events – male participants

3.4.2 VISIT WINDOWS FOR MALE PARTICIPANTS

The ADVANCE-D Programme takes 14 weeks to be delivered. The research will take place over 24 months. Participants will be followed-up 4-months (+/- 4 weeks) and 12-months (+/-4 weeks) post-baseline interview and 24-month follow up will be undertaken by tracking the cohort in routine health and social care, and criminal justice databases.

3.4.3 SCREENING & ELIGIBILITY RISK ASSESSMENT FOR MALE PARTICIPANTS

Eligibility screening will be undertaken by PP/ JSW at PDU/ JSWT (Contact 1). During this contact, PP/ JSW will also conduct the risk assessment to determine suitability.

3.4.4 CONSENT FOR MALE PARTICIPANTS

PP/ JSW will gain informed consent from approximately 14 participants per PDU/JSWT to take part in the trial. The number of men a PDU/JSWT will consent before transferring details to the Trial Manager is estimated to be approximately 14, but will be decided ad hoc per site depending on recruitment levels. Once all men from a cluster have been consented, PP/ JSW will securely inform the trial manager of the contact details of the consented individuals and their (ex)-partners using a password protected document via encrypted e-mail, a secure Microsoft Teams channel or via another secure method (e.g. Criminal Justice Secure Email) (contact 2). Only one cluster will be recruited from each PDU/JSWT.

3.4.5 BASELINE VISIT FOR MALE PARTICIPANTS

The trial manager will allocate consented men to researchers to conduct the baseline interview by phone or video call or in person at the PDU/ JSWT within two weeks of all men in the cluster being consented.

During contact 3, consented participants will be called by the researcher to arrange a convenient time for the baseline interview. During the call/meeting the researcher will:

- 1. Confirm willingness to participate.
- 2. Re-explain PIS (participant will already have a copy prior to consenting).
- 3. Arrange a convenient time to call/ meet to conduct the baseline interview.

During this call/ meeting to conduct the baseline interview (contact 4), the researcher will:

- 1. Re-explain the PIS and check consent.
- 2. Register the participant into the study (initials and age required).
- 3. Provide contact details of support services for IPV perpetration and substance use.
- 4. Complete the baseline interview.

Baseline data collected from participants using the following assessment tools. For IPV perpetration: (Adapted) Abusive Behavior Inventory (ABI) [primary outcome], (Adapted) Revised Controlling Behaviors Scale (CBS-R), technology facilitated abuse, locked-in, stalking/harassment, using children against partner, (Adapted) Intimate Partner Violence Responsibility Attribution Scale (IPVRAS); Alcohol Use Disorder Identification Test (AUDIT), Drug Use Disorder Identification Test (DUDIT), Treatment Outcomes Profile (partial) (substance use free days); Patient Health Questionnaire (PHQ-9) (depression), Generalised Anxiety Disorder symptoms (GAD-7) (anxiety), Primary Care PTSD Screen for DSM-5 (PC-PTSD-5), Propensity for Abusiveness Scale (PAS) (anger), Brief Self-Control Scale (BSCS) (self-control); EQ-5D-5L (Quality of Life), children's well-being, service use and medication.

3.4.6 4 MONTH FOLLOW-UP VISITS FOR MALE PARTICIPANTS

Four months post baseline interview, participants will be called by the researcher to arrange a convenient time for the 4-month follow-up interview (contact 5). During the call/meeting, the researcher will:

- 1. Confirm willingness to participate.
- 2. Re-explain what the interview will entail.
- 3. Arrange a convenient time to call/ meet to conduct the 4-month follow-up interview (contact 6).

During this call/ meeting to conduct the 4-month follow-up interview (contact 6), data will be collected from participants using the following assessment tools. For IPV perpetration: (Adapted) ABI [primary outcome], (Adapted) CBS-R, technology facilitated abuse, locked-in, stalking/harassment, using children against partner, (Adapted) IPVRAS; Treatment Outcomes Profile (partial) (substance use free days); PHQ-9 (depression), GAD-7 (anxiety), PC-PTSD-5, PAS (anger), BSCS (self-control); EQ-5D-5L (Quality of Life), children's well-being, service use and medication. Participants in the intervention clusters will also be asked to complete the (Adapted) Working Alliance Inventory applied to Virtual and Augmented Reality (WAI-VAR) and the (Adapted) California Psychotherapy Alliance Scale-Short Form (CALPAS-P).

A purposively selected sample (age, IPV type, area, lives with partner, has children) of 40 participants, their (ex)-partners and the facilitators delivering ADVANCE-D will be invited to participate in a brief qualitative interview to explore their experience of taking part in the intervention and any impact on their relationship (see process evaluation). This interview can be undertaken during contact 6 or arranged for a separate time.

3.4.7 12 MONTH FOLLOW-UP VISITS FOR MALE PARTICIPANTS

Twelve months post baseline interview, participants will be called by the researcher to arrange a convenient time for the 12-month follow-up interview (contact 7). During the call/meeting the researcher will:

- 1. Confirm willingness to participate.
- 2. Re-explain what the interview will entail.
- 3. Arrange a convenient time to call/ meet to conduct the 12-month follow-up interview (contact 8).

During this call/ meeting to conduct the 12-month follow-up interview (contact 8), data will be collected from participants using the following assessment tools. For IPV perpetration: (Adapted) ABI [primary outcome], (Adapted) CBS-R, technology facilitated abuse, locked-in, stalking/harassment, using children against partner, (Adapted) IPVRAS; AUDIT, DUDIT, Treatment Outcomes Profile (partial) (substance use free days); PHQ-9 (depression), GAD-7 (anxiety), PC-PTSD-5, PAS (anger), BSCS (self-control); EQ-5D-5L (Quality of Life), children's well-being, service use and medication.

The same purposively selected sample of participants described above will be invited to participate in a brief qualitative interview to explore their experience of taking part in the intervention and any impact on their relationship (see process evaluation). This interview can be undertaken during contact 8 or arranged for a separate time.

3.4.8 ADVANCE-D PROGRAMME

ADVANCE-D is a 14 week, 33 session programme that consists of an individual goal setting session with the facilitator, a welcome to ADVANCE-D group, a follow-up call post group, 6 group sessions (one each fortnight), 12 self-complete website sessions (one a week) and 12 invidual coaching sessions with a facilitator (one a week). One month after the last group session, a booster group will be held. ADVANCE-D website sessions are available in Polish, Romanian, Urdu, or Panjabi to allow participants to complete it in their first language.

3.4.9 CURRENT OR EX-PARTNERS OF MEN IN THE TRIAL

Timepoint																				9	a
	Week 0	Week 1	Week 2	Week 3	Week 4	Week 5	Week 6	Week 7	Week 8	Week 9	Week 10	Week 11	Week 12	Week 13	Week 14	Week 15	Week 16	Week 20	Month 4 post baseline	Month 12 post baseline	Month 24 post baseline
1. Introductory call		X																			
2. Screening and eligibility		X																			
3. Registration and consent			X																		
4. Baseline			X																		
5. ADVANCE-D																					
a. Initial contact from partner support worker				X																	
b. Risk assessment					X																
c. Weekly support from partner support worker						X	X	X	X	X	X	X	X	X	X	X	X				
d. Weekly access to ADVANCE-D website						X	X	X	X	X	X	X	X	X	X	X	X				
6. Follow-up assessment																			X	X	
7. Data linkage with health and criminal justice records																					X

Table 4. Schedule of events – current or ex-partners of men in the trial

3.4.10 VISIT WINDOWS FOR CURRENT OR EX-PARTNERS

The research will take place over 24 months. (Ex)-partners of men in the trial will be followed-up 4-months (+/- 4 weeks) and 12-months (+/- 4 weeks) post-baseline interview and 24-month follow up will be undertaken by tracking the cohort in routine health and social care, and criminal justice databases. Research contacts/visits will take place in person or by phone/video call. Research interviews will never be conducted in participants' or (ex)-partners' homes.

3.4.11 Introductory call, Screening & eligibility of current or ex-partners

Researchers will initially send a text to current or ex-partners of men in the trial to inform them they will ring them to invite them to take part in the research (contact 1) and arrange a time for an introductory call. During the introductory call (contact 2) researchers will:

- 1. Inform them their (ex)-partner is participating in the study.
- 2. Read the PIS, explain what taking part involves.
- 3. Invite them to participate in the research (baseline and follow up interviews).
- 4. Advise them that an integrated support service (ISS) worker will call to offer them support only if their current or ex-partner is allocated to receive the ADVANCE-D Programme.
- 5. Arrange a convenient time to call/ meet to conduct the baseline interview (contact 3)

If (ex)-partners are interested, researchers will send a message on WhatsApp, email or post a copy of the PIS and consent form.

3.4.12 CONSENT AND BASELINE INTERVIEW WITH CURRENT OR EX-PARTNERS

A different researcher from the researcher who conducted the interview with the male participant (to avoid inadvertant disclosure of information) will gain consent or check consent (if eConsent given) and conduct the baseline interview (contact 3). The researcher will:

- 1. Gain informed consent (audio or written) or check willingness to participate if consent already received (eConsent or by post).
- 2. Re-explain PIS (participant will already have a copy prior to consenting).
- 3. Register the participant into the study (initials and age required).
- 4. Provide contact details of support services for IPV perpetration and substance use.
- 5. Complete the baseline interview.

Researchers will collect baseline data from current or ex-partners using the following assessment tools. For IPV victimisation: (Adapted) ABI-R, (Adapted) CBS-R, technology facilitated abuse, locked-in, stalking/harassment, using children against partner; feeling of safety, AUDIT, DUDIT, Treatment Outcomes Profile (partial) (substance use free days); PHQ-9 (depression), GAD-7 (anxiety), PC-PTSD-5; EQ-5D-5L (Quality of Life), children's well-being, service use and medication.

3.4.13 4 MONTH FOLLOW-UP VISITS FOR CURRENT OR EX-PARTNERS

Four months post baseline interview, current or ex-partners will be called by the researcher to arrange a convenient time for the 4-month follow-up interview (contact 4). During the call/meeting, the researcher will:

- 1. Confirm willingness to participate.
- 2. Re-explain what the interview will entail.
- 3. Arrange a convenient time to call/ meet to conduct the 4-month follow-up interview (contact 5).

During this call/ meeting to conduct the 4-month follow-up interview (contact 5), data will be collected from participants using the following assessment tools. For IPV victimisation: (Adapted) ABI-R, (Adapted) CBS-R, technology facilitated abuse, locked-in, stalking/harassment, using children against partner, feeling of safety; Treatment Outcomes Profile (partial) (substance use free days); PHQ-9 (depression), GAD-7 (anxiety), PC-PTSD-5; EQ-5D-5L (Quality of Life), children's well-being, service use and medication.

Current or ex-partners of men purposively selected for the longitudinal qualitative interviews will be invited to participate in a brief qualitative interview to explore their experience of taking part in the intervention and any impact on their relationship (see process evaluation). This interview can be undertaken during contact 5 or arranged for a separate time.

3.4.14 12 MONTH FOLLOW-UP VISITS FOR CURRENT OR EX-PARTNERS

Twelve months post baseline interview, current or ex-partners will be called by the researcher to arrange a convenient time for the 12-month follow-up interview (contact 6). During the call/meeting, the researcher will:

- 1. Confirm willingness to participate.
- 2. Re-explain what the interview will entail.
- 3. Arrange a convenient time to call/ meet to conduct the 12-month follow-up interview (contact 7).

During this call/ meeting to conduct the 4-month follow-up interview (contact 7), data will be collected from participants using the following assessment tools. For IPV victimisation: (Adapted) ABI-R, (Adapted) CBS-R, technology facilitated abuse, locked-in, stalking/harassment, using children against partner; feeling of

safety, AUDIT, DUDIT, Treatment Outcomes Profile (partial) (substance use free days); PHQ-9 (depression), GAD-7 (anxiety), PC-PTSD-5; EQ-5D-5L (Quality of Life), children's well-being, service use and medication.

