Note: A court can impose a DRR for any substance that is included in the Misuse of Drugs Act 1971. It is up to the court to decide Note: A court can impose a DRR for any substance that is included in the Misuse of Drugs Act 1971, it is up to the court to decide if they think that any substance used by a person is covered by this. However, a DRR can only be imposed if there is a test for the drug of choice available in the community. There is no test routinely available for Psychoactive Substances (PS) in the community currently. The court would need to be advised that making a person who only used PS subject to a DRR would not meet the requirements to impose such an intervention. Most people are poly drug users. If someone presents as using any substance that can be tested for (Opiates, Occaine, Amphetamines, Beroodiazepine and Cannabis) in combination with the above, a DRR can be recommended if agreed with a Treatment Provider.

[figure not shown]
Table 2. Suitability screening tool for substance use interventions

Probation Practitioners (England)/ Justice Social Workers (Scotland) check men's eligibility

In England, Probation Practitioner completes Offender Assessment System (OASys), SARA v2 and sentence planning. In Scotland, Justice Social Workers complete Level of Service/Case Management Inventory (LS/CMI), SARA v3 and sentence planning. Identification of men can also be done retrospectively.

- Adult (18+) men serving a community sentence or post imprisonment on license for IPV towards a female current or ex-partner
- Drugs or alcohol linked to criminogenic need recorded on OASys (England) or LS/CMI (Scotland)
- Able to provide contact details for (ex)-partner victim of index crime will be invited to participate in the trial
- Able to communicate in and understand English for the purpose of research interviews
- No history of sex offences against children
- Answers 'strongly disagree' to all 8 items on the eHealth Literacy Scale (eHEALS)
- Substance use does not impair ability to take part in the trial using the substance use screen (England) or SARA V3 (Scotland)
- Not suitable for existing probation-based perpetrator interventions
- Not involved with the private family law court

health, social and criminal justice data sets

Figure 3. Study flowchart

Figure 3 illustrates the different phases of the cRCT for male participants.

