8.2 PARTICIPANT DISTRESS PROTOCOL

Talking about past or current violence in a relationship may make participants feel upset. If this happens, participants will be given the opportunity to speak to a PP/JSW at the PDU/JSWT or to women's support services (women only) about how they feel if they wish to, at that time or in the future. All participants will be provided with a range of local contact numbers and services that will be able to help after each research assessment/interview. We have developed a distress protocol. If any participant (male or female) involved in the research becomes upset as a result of their involvement in the study, the researcher will:

- Stop the interview and provide sympathetic and non-judgemental recognition of any emotional distress the participant is expressing.
- Refer the participant back to their PP/ JSW; or women's support worker (if interviewed at a ISS).
- If a participant discloses an immediate intention to harm themselves or others, the *safeguarding protocol* will be followed (see under Limitations to Confidentiality above).
- The researcher will call the Chief Investigator ([name], KCL) on her mobile (or a designated deputy from the co-investigators if the Chief Investigator is on leave) to inform them of the event and the action taken.
- On returning to the office, an incident form describing the disclosure and the action taken will be completed by the researcher using only the participant ID. The Ethics Committee will be informed if the adverse event is serious.
- All incident forms will be stored on SharePoint. Incident forms contain only participant ID number not participant name.

Participants who have a court order preventing them or someone on their behalf from contacting a current or former partner (e.g. restraining order/bail restriction/exclusion order/non molestation order etc.) will be ineligible. This will be based on self-report by the perpetrator in the first instance (but confirmed where possible by his current or ex-partner and the substance use treatment service). The man's keyworker at the substance use treatment service will make the final decision on whether the man is suitable to take part in the study.

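### Women interviewed as victims are given contacts for perpetrator services, and a no-contact-order exclusion for men stands only in section 8.2, with a decision-maker who has no role in this trial

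*Protocol*

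**What the plan says.** **Contacts for women.** In Protocol 3.4.12, step 4 of the women's baseline interview tells the researcher: "Provide contact details of support services for IPV perpetration and substance use". The same step stands in 3.4.5 for the men. The paragraph after step 4 in 3.4.12 lists the women's measures under IPV victimisation.

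**No-contact orders.** Section 8.2, the participant distress protocol, says of "Participants who have a court order preventing them or someone on their behalf from contacting a current or former partner" that they "will be ineligible. This will be based on self-report by the perpetrator in the first instance". It adds that the partner and the substance use treatment service will confirm this where they can, and ends: "The man's keyworker at the substance use treatment service will make the final decision on whether the man is suitable".

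The nearest entry in the men's exclusion criteria (3.2.2) is item 2, "Man involved with the private family law court". Its counterpart in Figure 3 is "Not involved with the private family law court".

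Item 3 of the women's exclusion criteria (3.2.4) covers this case: "Female partner discloses that there is an order preventing her male current or ex-partner from contacting her". It describes her account as contradicting the man's answer at screening, and continues: "In such cases the man would not be withdrawn, unless the clinical team felt there was an increased risk to either party".

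**The concern.** A woman about to be asked about violence against her should be given details of services for victims. As written, the step gives her details of services for people who commit it. The substance use half of the step is appropriate, since women also complete the substance use measures.

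The court-order rule matters more because it decides who enters the trial. Eligibility rules are applied from the eligibility section, and this one sits at the end of a section on handling distress. A probation practitioner (PP) or justice social worker (JSW) screening from section 3.2 has no prompt to ask about orders. The person 8.2 names to decide is not part of the trial's structure, and some men may have no such person. Sites could then apply different entry rules in a population of men sentenced for IPV whose victim is to be contacted.

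**Working it through.** There is no figure to reproduce. The check is a comparison of sections and a count.

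**1. Contacts.** The steps in 3.4.5 (men) and 3.4.12 (women) have identical wording. Women join as the victim of the index offence (3.2.3 and 3.3), and Table 5 assigns perpetration measures to men and victimisation measures to women. The men's wording therefore does not fit the women's interview.

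**2. Where the order rule appears.**

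| Place | Entries | Entries on a no-contact order for the man |
|---|---|---|
| 3.2.1 inclusion, men | 4 | 0 |
| 3.2.2 exclusion, men | 5 | 0 |
| 3.2.1 + 3.2.2 | 4 + 5 = 9 | 0 |
| Synopsis, men's criteria | the same 9 | 0 |
| Figure 3, eligibility lines that can be read | 9 | 0 |
| 8.2 | 1 exclusion rule | 1 |

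The family-court criterion does not fill the gap. It concerns involvement in a type of proceedings and names no order. Item 1 of 3.2.4 concerns an order that binds the woman, and it excludes her, not the man.

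**3. Who decides.** Section 3.1 makes Probation Delivery Units and Justice Social Work teams (PDU/JSWT) the clusters. Section 3.4.3 gives eligibility screening to the PP/JSW. Section 4.3 only permits treatment for substance use, so a man may enter with no treatment service and no keyworker there. The wording looks like a leftover: section 1.1 says that ADVANCE was first developed and tested with men in substance misuse treatment. Section 8.3 likewise names treatment-service staff for safeguarding discussions, though it also gives the ADVANCE-D clinical lead, so a valid contact remains there.

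**4. What a screener would do.** A man under a no-contact order who meets all 4 inclusion criteria and none of the 5 exclusion criteria is eligible under section 3.2. Under 8.2 the same man is ineligible. The protocol does not say which section prevails.

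**5. How many men.** The protocol gives no rate of such orders, so no estimate can be made.

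**The case against.** The strongest reply is that these are clerical slips with little practical effect. On contacts, the opening of 8.2 promises every participant local contact numbers after each interview, so a woman would still receive suitable details. That stands and limits the harm, but step 4 still names the wrong service. On orders, 3.4.3 has the PP/JSW carry out a risk assessment as well, so the list in 3.2 is not the only gate, and operating procedures outside the protocol may ask the question. That is possible, but neither supplies the missing criterion or a valid decision-maker. Figure 3 is also only partly legible here, so its count is weak evidence; the lists in 3.2.1 and 3.2.2 carry the point without it.

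A reader might infer two stronger points that the protocol does not support.

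- **That 3.2.4 item 3 contradicts 8.2**, because it keeps in the trial a man whom 8.2 would exclude. The sequence answers this. Under 5.3.2 a man is enrolled when he signs consent, and under 3.3 and 3.7.1 his partner is approached only after his baseline interview. Her disclosure to researchers therefore comes after he has enrolled, and item 3 is worded in terms of withdrawal and continuing. Section 8.2 governs entry; item 3 governs what follows if an order comes to light later.
- **That the distress procedure leaves most women without a suitable contact**, because one bullet in 8.2 names a women's worker only for interviews held at the integrated support service. The opening of the same section offers women's support services without that condition, and 8.1 names the women's support worker for disclosures of serious risk.

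**Conclusion.** Two statements are wrong as written. Step 4 of 3.4.12 names the wrong type of service for women. Section 8.2 holds an eligibility rule for men that appears in 0 of their 9 listed criteria, and assigns the decision to someone outside the trial. The second matters more, since a man can be enrolled correctly under section 3.2 and still be ineligible under 8.2.

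The severity is minor. Arms, outcomes, sample size and analysis are untouched. The conclusion assumes that 8.2 is meant to apply in this trial. Item 3 of 3.2.4 supports that assumption, because it presupposes that the man was asked about orders at screening.

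**What to change.** 1. In 3.4.12 step 4, write *support services for IPV victims/survivors and substance use*.
2. Add the no-contact-order exclusion to 3.2.2, the synopsis and Figure 3. This agrees with the reference in 3.2.4 item 3 to the man's screening answer.
3. In 8.2, replace the treatment-service keyworker with the PP/JSW, together with the ADVANCE-D clinical lead, as the final decision-maker. Cross-refer to 3.2.2 so that the rule is stated once.
4. In 8.3, replace the treatment-service staff with PDU/JSWT staff and keep the clinical lead.

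The cost is a wording amendment and one extra line on the screening form. Listing the exclusion may make sites apply a rule they do not apply now, which could slightly reduce recruitment towards the 450 men planned. The protocol gives no figure from which to size that loss.
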